**Effects of 12-week Aerobic Exercise on Arterial Stiffness,
Inflammation, and Cardiorespiratory Fitness in Women with Systemic
LUPUS Erythematosus: Non-Randomized Controlled Trial**

NCT: NCT03107442

Document Date: 26/03/2024

Study Protocol and Statistical Analysis Plan

1. Objective

The primary aim of this study was to assess the effect of a 12-week aerobic exercise intervention following the ACSM guidelines on arterial stiffness in women with SLE in comparison with usual care. Secondary aims were to assess the effects of the exercise intervention on inflammation, oxidative stress, and cardiorespiratory fitness.

2. Design and Protocol Registration

This non-randomized controlled trial was registered at clinicaltrials.gov [NCT03107442] on 11 April 2017, before the enrolment of participants started (i.e., on 12 April), and no deviations occurred regarding the primary outcome and the secondary outcomes analyzed here.

3. Setting and Eligibility Criteria

Participants were recruited from the Systemic Autoimmune Diseases Unit of the “Virgen de las Nieves” and the “San Cecilio” University Hospitals. Women with a diagnosis of SLE according to the ACR criteria [26], a follow-up of 12 months, clinical and treatment stability during the previous six months, and not performing regular exercise (defined as 60 min/week of structured exercise) were included. Exclusion criteria were to have been under biological treatment in the previous six months or to need a prednisone dose of >10 mg/day; a background of CVD in the previous year; to present contraindications to perform exercise; other associated rheumatic conditions; pregnancy; active acute or chronic infection; neoplasms; acute renal failure; cardiac or pulmonary involvement; body mass index (BMI) >35; or not being able to read, understand, and sign written informed consent.

All participants received detailed information about the study procedures, and signed written informed consent. The Research Ethics Committee of Granada approved the protocol on 11 November 2016 (reference No.: 10/2016).

4. Procedures

A telephone screening was conducted. Potentially eligible participants were invited to a personal screening and, if included, day 1 of the baseline examination was performed. The baseline examination comprised two assessment days. On day 1, pulse wave velocity (PWV) was assessed. Thereafter, cardiorespiratory fitness testing was performed, and socio-demographic and clinical information was collected. On day 2 (i.e., between two and four days after day 1), 8-h fasting blood samples were collected between 8:00 a.m. and 10:00 a.m. This article follows the TREND statement for improving the reporting of non-randomized experiments of behavioral and public health interventions (downloadable at EQUATOR Network: <https://goo.gl/ZSyLrj>; Supplementary Table S1) [27]. The funding source had no role in the study.

5. Methods

5.1. Interventions

5.1. 1. Exercise Group

To maximize transparency and replicability, the exercise program described in this manuscript follows the Consensus on Exercise Reporting Template (CERT; Supplementary Table S2) [28]. The patients assigned to exercise performed two 75-min sessions per week during a total of 12 weeks (i.e., 24 sessions) of moderate to vigorous intensity aerobic exercise on a treadmill (BH, Serie i.RC12 Dual, Vitoria-Gasteiz, Spain) from 24 April to 14 July 2017. The sessions took place in a quiet room of the “Virgen de las Nieves” Hospital, Granada (Spain).

All sessions were performed in groups of a maximum of five persons (depending on the patients’ schedule preferences) and were supervised by both exercise professionals with a degree in Sports Sciences and residents from the Internal Medicine Department.

Attendance at the sessions was registered daily and patients were contacted upon any missing session to ask for the reason and motivate them to replace it on an alternative day of the same week. Adherence to exercise is reported as the median attendance frequency and the proportion of patients attending >75% (i.e., 18 sessions; the minimum pre-defined attendance to assess efficacy) and >90% of the sessions. All the sessions began with a warm-up comprising 3–4 min of activation on the treadmill at about 35–40% of the heart rate reserve (HRR) and 3–4 min of active stretching of major muscle groups, and ended with a cool down phase of static stretching of major muscle groups and relaxation. Exercise was individually prescribed to represent moderate-to-vigorous intensity, with training intensity ranging from 40% to 75% of each patient's HRR. The maximum heart rate (HRmax) was estimated with the formula by Tanaka et al. ($HRmax = 208 \times (0.7 \times \text{age})$) [29]. The training (or target) heart rate (tHR) was calculated with the formula $tHR = HRrest + (%HRR)$. Heart rate was continuously monitored during all sessions (Polar V800, Kempele, Finland). We used the session rating of perceived exertion (RPE) as a measure of subjective training load [30], and the feeling scale to assess positive affective responses experienced before and after each session [31].

The starting level was specific for each individual according to her previous exercise experience and physical fitness. During the first half of the program, only continuous exercise was performed so that the patients got used to the treadmill and felt confident at increasing intensities. Continuous sessions comprised several bouts of exertion at constant intensity, followed by a couple of minutes of recovery (i.e., rest) to drink water. During month 2, there were alternated continuous and interval sessions, and at month 3, the patients undertook interval training sessions, where there were periods of lower and periods of higher intensity efforts followed by some minutes of rest for hydration (Table 1). The progression in volume and/or intensity was patient-limited and was undertaken by increasing the treadmill speed (first) or inclination according to the symptoms and perceived exertion. There were no home-based or non-exercise components within this intervention. However, if a participant was eventually not able to attend a particular session, we provided

her with a heart rate monitor and allowed recovery of that session out of the Hospital (a total of seven sessions were recovered in this fashion). Finally, the exercise intensity progressions had to be slightly modified from the initial plan. For instance, several patients perceived a 5% HRR intensity increase (i.e., from one week to another) as very heavy and difficult-to-follow. Consequently, there were weeks in which exercise intensity increased by 2.5% instead of 5% (Table 1).

5.1.2. Control Group

After the baseline evaluation, the SLE patients assigned to the (usual care) control group received verbal information about a healthy lifestyle, including physical activity guidelines and basic nutritional information.

5.2. Outcome Measures

Primary Outcome Measure: Arterial Stiffness

Arterial stiffness was assessed in a sitting position by PWV [9], using the Mobil-O-Graph® 24 h pulse wave analysis monitor (IEM GmbH, Stolberg, Germany), whose operation is based on oscillometry recorded by a blood pressure cuff placed on the brachial artery. The coefficient of variation (CV) of Mobil-O-Graph for consecutive PWV analyses is 3.4% and its intraclass correlation coefficient is 0.98 [0.96–0.99] [32]. This device has been largely shown to be valid and reliable for measuring PWV and central blood pressure in different populations [33,34], meets the accuracy requirements of the

British Hypertension Society (BHS) standard [35], and can be recommended for clinical use [36].

Secondary Outcome Measures

Blood Samples and Biochemical Analyses

Fasting blood specimens for biochemical and immunological tests were collected and routinely processed by the central laboratory of our hospital. Among other measurements, they included lipids, insulin (BioRad, Marne-la-Coquette, France), and a routine biochemical profile. The homeostatic model assessment for insulin resistance (HOMA-IR) was calculated (HOMA-IR = glucose (mmol/L) × insulin (U/L)/22.5).

Inflammatory Markers Serum high-sensitivity CRP was assessed by an immunoturbidimetric method using the ARCHITECT cSystems (MULTIGENT CRP Vario assay); the limit of quantitation was 0.2 mg/L and the upper limit for normal serum was 5 mg/L (coefficient of variation <6%). Interleukin 6 and TNF-, as well as myeloperoxidase (MPO; as marker of oxidative stress), were measured in plasma. Serum was initially separated by centrifugation and stored at $\square 70\text{ C}$.

Bioserum concentrations of IL-6/TNF- (pg/mL) and MPO (ng/mL) were measured by an immunoradiometric assay using commercial kits (MILLIPLEX MAP Kit Human High Sensitivity T Cell Magnetic Bead Panel (HSTMAG-28SK) and Human Cardiovascular Disease Magnetic Bead Panel 2 (HCVD2MAG-67K)), Millipore) following the manufacturer's instructions. Quantitative data were obtained by using the Luminex-200 system (Luminex Corporation, Austin, TX, USA), and data analysis was performed on Xponent 3.1 software (Austin, TX, USA). The detections limits were 0.73 pg/mL for IL-6, 0.43 pg/mL for TNF-a, and 0.024 ng/mL for MPO.

Cardiorespiratory Fitness

Cardiorespiratory fitness was assessed with the Bruce submaximal treadmill protocol [37]. The test comprised five increasing workload stages of 3 min each (stage 1: 2.7 km/h and 10% inclination; stage 2: 4 km/h and 12% inclination; stage 3: 5.5 km/h and 14% inclination; stage 4: 6.8 km/h and 16% inclination; stage 5: 8 km/h and 18% inclination). The test concluded when the participant achieved 85% of the individual's HRmax, as

estimated with the formula by Tanaka et al. [29]. As validated SLE-specific formulas to estimate VO₂max are not available, we used the total time to reach 85% HRmax as the outcome of interest.

Other Measurements

All participants filled out a socio-demographic and clinical data questionnaire. Height (cm) was measured using a height gauge, weight (kg) with a bioimpedance device (InBody R20, Biospace, Seoul, Korea), and body mass index (BMI) was calculated (kg/m²). Blood pressure was measured with Mobil-O-Graph® (IEM GmbH, Stolberg, Germany) [36]. Disease activity was assessed through the Systemic Lupus Erythematosus Disease Activity Index (SLEDAI, range 0–105 where a higher score indicates higher degree of disease activity). Physical activity was self-reported at baseline and at week 12 with the International Physical Activity Questionnaire [38].

Sample Size

The sample size was calculated for the primary outcome (i.e., PWV). Ashor et al. found an average effect of aerobic exercise on PWV of $\square 0.63$ m/s in adults aged ≥ 18 years [21]. A total of 52 patients (26 per group) were needed to detect an effect of $\square 0.63$ (SD 0.75) m/s, with a power of 85% and an error of 0.05. Anticipating a maximum loss to follow-up of 15%, we aimed at recruiting a total of 60 patients.

Treatment Allocation and Blinding

Randomization was not feasible because more than half of the patients who regularly attend the Autoimmune Disease Units lived far from the Hospital and were not able to attend twice per week in case of being randomized to exercise. Therefore, participants from the city of Granada were included in the exercise group and participants living outside Granada were included in the control group.

To minimize potential selection bias, we aimed to match the groups by age (2 years), BMI (1 kg/m²), and SLEDAI (1 unit). The data analyzer was blinded to the patient allocation.

Statistical Analysis

The distribution of the main study variables was assessed through histogram and Q-Q plots. As the main outcomes were non-normally distributed, their descriptive characteristics were presented using the median and interquartile range instead of the mean and standard deviation and we used non-parametric tests for the main analyses. Between-group baseline characteristics were compared with the Student t-test (when normally distributed) or Kruskal-Wallis test (when non-normally distributed) for continuous variables and the Chi-square test for categorical variables. The between-group differences in the studied outcomes were assessed through quantile regression with baseline values, resting heart rate (bpm) [39], and changes in physical activity (min/week; since the change in self-reported physical activity at week 12 was >60 min higher in the control compared to the exercise group and this change was associated with changes in PWV; rPearson = 0.27, p = 0.048) as potential confounders, after checking baseline group comparisons. As we aimed at assessing efficacy, the primary analyses were defined as per-protocol, where patients from the exercise group were included if attendance at the exercise sessions was 75%. To assess the robustness of the results, subsequent sensitivity analyses (i.e., baseline observation carried forward (BOCF) imputation; per-protocol with minimum attendance of 90%, and complete-case analyses) were conducted. A blinded investigator ([name]) undertook the data handling and all hypothesis testing. All the

analyses were conducted with Stata v.13.1 (StataCorp LP., College Station, TX, USA).

Statistical significance was set at $p < 0.05$.

Results

There were no between-group differences in the changes in arterial stiffness (median PWV difference $\Delta 0.034$, 95% CI $\Delta 0.42$ to 0.36 m/s; $p = 0.860$) or hsCRP, TNF-, IL-6, and MPO (all $p > 0.05$) at week 12. In comparison to the control group, the exercise group significantly increased cardiorespiratory fitness (median difference 2.26 minutes, 95% CI 0.98 to 3.55; $p = 0.001$). These results suggest that 12 weeks of progressive treadmill aerobic exercise increases cardiorespiratory fitness without exacerbating arterial stiffness, inflammation, or oxidative stress in women with SLE.

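### Does the stated 85% power need to be re-derived or qualified because the primary analysis is a per-protocol quantile regression rather than a comparison of means?

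*Combined protocol and SAP*

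**What the plan says.** The Sample Size paragraph takes an average effect of aerobic exercise on PWV of 0.63 m/s from a published source and states: "A total of 52 patients (26 per group) were needed to detect an effect of" that size, with the assumptions "SD 0.75) m/s, with a power of 85% and an error of 0.05". It continues: "Anticipating a maximum loss to follow-up of 15%, we aimed at recruiting a total of 60 patients". It does not name the test, say whether it is one- or two-sided, say whether the SD is of PWV or of its change, or say whether the 52 are patients remaining after any attendance exclusion.

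The Statistical Analysis section describes a different model: "The between-group differences in the studied outcomes were assessed through quantile regression", adjusted for baseline value, resting heart rate and change in self-reported physical activity. The reason given is that the main outcomes were not normally distributed. The primary analysis set is per-protocol and keeps exercisers who met a 75% attendance threshold, which section 5.1.1 (Exercise Group) calls "the minimum pre-defined attendance to assess efficacy".

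The same section shows that attendance was actively protected: "patients were contacted upon any missing session to ask for the reason and motivate them to replace it". Sessions could also be made up outside the hospital, and "a total of seven sessions were recovered in this fashion".

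**The concern.** Three features suggest that the power statement does not fit the analysis. First, an average effect with an SD points to a test of means, whereas the reported PWV result is a median difference from quantile regression. With normal errors a sample median is less efficient than a mean, so the same 26 per group would give less than 85%. Secondly, the primary set drops exercisers with low attendance under a rule called pre-defined, so such exclusions could have been foreseen, yet the recruitment target is justified by loss to follow-up alone. Thirdly, 60 less 15% is 51, one short of 52.

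The stake is how the null PWV result is read. This is the only power figure in the document. A reader may take the absence of a difference (p = 0.860) as the outcome of an 85%-power test of 0.63 m/s. If the real power had been much lower, that reading would be too confident.

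**Working it through.** **Inputs.** From Sample Size: difference 0.63 m/s, SD 0.75 m/s, power 85%, alpha 0.05, 26 per group, 15% loss, 60 recruited. From Statistical Analysis: r = 0.27 with p = 0.048 for change in activity against change in PWV. From Results: median difference 0.034 m/s, interval limits 0.42 and 0.36 m/s, p = 0.860. Minus signs were lost in text extraction. Only -0.42 gives an ordered interval, and its midpoint, (-0.42 + 0.36)/2 = -0.03, agrees with -0.034.

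**1. The plan's own figure.** For two means, n per group = 2(z₁ + z₂)²SD²/d².
- Two-sided: 2 × (1.960 + 1.036)² × 0.75²/0.63² = 25.45, so 26 per group and 52 in total, as stated.
- One-sided: 2 × (1.645 + 1.036)² × 0.75²/0.63² = 20.4, so 21, which does not match.
- At 26 per group the standard error is 0.75 × √(2/26) = 0.208. Power is Φ(0.63/0.208 - 1.960) = 85.7%, or 84.4% by the t-test.

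The arithmetic is sound. That it is a two-sided comparison of means is inferred from the exact match.

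**2. The recruitment target.** 52 × 1.15 = 59.8, which rounds to 60. Dividing instead, 52/0.85 = 61.2. A 15% loss from 60 leaves 51. With 25 and 26 patients, power is 85.1% (83.6% by the t-test). The formula needs only 2 × 25.45 = 50.9 patients, so the missing patient costs nothing that matters.

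**3. Attendance exclusions.** No rate is given, so only break-even counts are possible. Assume 30 recruited per group and the means formula.

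| Exercise / control | Power |
|---|---|
| 30 / 30 | 90.2% |
| 23 / 30 (7 excluded, no other loss) | 85.8% |
| 22 / 30 (8 excluded, no other loss) | 84.9% |
| 24 / 26 (15% lost, then 1 excluded) | 84.3% |
| 20 / 26 (15% lost, then 5 excluded) | 80.6% |
| 19 / 26 (15% lost, then 6 excluded) | 79.5% |

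Patients lost and patients excluded may be the same people, so the lower rows are pessimistic.

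**4. Median instead of mean.** With asymptotic efficiency e of the median relative to the mean, the standard error becomes 0.208/√e. The error shapes are assumptions, at 26 per group with no gain from covariates.

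| Error shape | e | Power |
|---|---|---|
| Normal | 0.637 | 67.6% |
| Logistic | 0.822 | 78.4% |
| Log-normal (sigma 0.5) | 0.929 | 83.1% |
| t with 3 df | 1.621 | 97.1% |
| Laplace | 2.0 | 99.0% |

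Simulated median regression with three covariates gave 58% to 88% over the same shapes. With normal errors and baseline correlations of 0.5, 0.6 and 0.7 it gave 70%, 76% and 86%. These simulations are indicative only: type I error was 0.027 to 0.033 rather than 0.05, so they understate power, and some fits reached the iteration limit. Error shape and covariate correlation are not in the documents, so neither the direction nor the size of any departure from 85% can be derived.

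**5. Precision achieved.** The interval's half-width is (0.36 + 0.42)/2 = 0.39, so the standard error is 0.39/1.960 = 0.199. As a check, 0.034/0.199 = 0.171 gives p = 0.864, close to the reported 0.860. The achieved 0.199 compares with 0.208 planned, and with 0.208/√0.637 = 0.261 had the full normal-errors penalty applied at SD 0.75. For the planned effect, power at this precision is Φ(0.63/0.199 - 1.960) = 88.6%. The interval also stops at -0.42, which is 0.63 - 0.42 = 0.21 m/s short of the planned reduction.

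**6. Numbers analysed.** After allowing for rounding, r = 0.27 with p = 0.048 is compatible with 52 to 56 patients. The set used for that correlation is not stated, but nothing here suggests an analysis on far fewer than 52.

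**The case for a change.** The strongest case for acting is that a planning figure should describe the analysis it supports. The attendance rule is called pre-defined, so exclusions could have been allowed for. A check on achieved precision comes after the event and cannot turn a calculation for means into one for quantile regression. The primary result is null, so the power figure will be read as reassurance, and a sentence of explanation costs almost nothing.

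Part of this stands. The 85% is not specifically established for the primary model, and the paragraph leaves the test, its sidedness and the meaning of the SD unstated.

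The rest carries less weight. The switch to non-parametric methods is explained by the distribution of the outcomes, and the activity covariate by a change seen at week 12; a calculation made before the trial could not have anticipated either. Sizing on means and then analysing by a robust method is common practice. It is also not known that the 52 ignores attendance, since the paragraph says only that this many were needed to detect the effect, which could mean analysable patients.

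Allocation was by residence ("participants from the city of Granada were included in the exercise group and participants living outside Granada were included in the control group"), so the interval does not cover confounding, nor selection by attendance. That limits the inference but is a separate matter from power.

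**Conclusion.** No change is needed. The mismatch between the sizing formula and the primary model is real, but it is missing detail rather than an error. The stated 26 per group and 85% are arithmetically correct for a two-sided comparison of means, and 60 recruits less 15% still give 85.1% on that formula. For the model actually used, assumed scenarios span roughly 58% to 99%, so any replacement figure would rest on inputs that the documents do not supply.

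Enrolment and treatment are complete and results are reported, so the useful question is whether the PWV estimate is precise enough to speak to 0.63 m/s. It is: the standard error is about 0.199 against 0.208 planned, and the interval excludes a 0.63 m/s reduction. As far as sampling error goes, low power for that effect does not explain the null result.

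This rests on three assumptions: the lost sign is a minus, the reported interval comes from the primary per-protocol model (the Results section does not say so explicitly), and a normal approximation serves to recover the standard error. A reader who takes the PWV result from its confidence interval rather than from the planned power is not misled. Naming the test would be harmless, but it would correct no figure and alter no analysis, result or conclusion.

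### The conclusion that exercise does not worsen inflammation or oxidative stress rests on non-significant comparisons, at the median as far as the text shows, which have very low power to reveal worsening in a minority of women

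*Combined protocol and SAP*

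**What the plan says.** The Statistical Analysis section gives one method for all outcomes: "The between-group differences in the studied outcomes were assessed through quantile regression with baseline values, resting heart rate (bpm", with change in physical activity as a further covariate. It names no quantile. The Results paragraph reports median differences for PWV and for fitness ("median difference 2.26 minutes, 95% CI 0.98 to 3.55; $p = 0.001"). The four markers are covered by a single statement that all p-values were above 0.05. The criterion is "Statistical significance was set at $p < 0.05", and no non-inferiority margin is given for any outcome. The closing sentence says that the programme "increases cardiorespiratory fitness without exacerbating arterial stiffness, inflammation, or oxidative stress in women with SLE".

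The primary analysis is per-protocol: exercise women count only if they met the attendance threshold. The sensitivity analyses (BOCF, a 90% attendance set, complete cases) change who is analysed or how gaps are filled. None is described as changing the quantile.

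Under Inflammatory Markers, the hsCRP assay description states that "the limit of quantitation was 0.2 mg/L and the upper limit for normal serum was 5 mg/L". The 5 mg/L figure does not appear again. SLEDAI is measured, but no week-12 SLEDAI analysis is described.

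**The concern.** Saying that exercise does not exacerbate inflammation is a statement about harm, and a reader will take it as reassurance for individual patients. In lupus, worsening may well be confined to some women. The median was chosen because the outcomes were non-normal. It resists extreme values, which suits an efficacy comparison of skewed markers. Here the same property works against the claim: a subgroup that worsens moves the median by a small, capped amount, however severe the worsening.

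The markers could therefore show no median difference while about five of 26 exercised women (20%) worsened sharply, and the printed conclusion would be the same. Supplying an interval or a margin for the median would not close this gap, because it would still describe only the centre of the distribution.

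**Working it through.** **Inputs from the documents.** Sample Size section: "A total of 52 patients (26 per group) were needed to detect an effect of" (minus) "0.63$ (SD 0.75) m/s, with a power of 85% and an error of 0.05", for PWV only, and "Anticipating a maximum loss to follow-up of 15%, we aimed at recruiting a total of 60 patients". There is no calculation for any marker.

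**The plan's own figure.** n per arm = 2 × (1.960 + 1.036)² × 0.75² / 0.63² = 2 × 8.98 × 0.5625 / 0.3969 = 25.4, so 26 per arm and 52 in total (two-sided). The stated 52 reproduces. The stated 60 equals 52 × 1.15; dividing 52 by 0.85 gives 62. The difference does not affect this point. The correlation reported in the Statistical Analysis section (r = 0.27, p = 0.048) fits about 54 analysed women, so 26 per arm is a fair basis.

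**Assumptions, since the documents give no marker distributions.** Changes are normal with SD 1. A share f of the exercise arm worsens by 3 SD. There are no covariates.

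**Step 1: how far the median can move.** If the harmed women move arbitrarily far, the arm's median becomes the 0.5/(1 − f) quantile of the unharmed women:

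- f = 10%: Φ⁻¹(0.5/0.9) = 0.14 SD
- f = 20%: Φ⁻¹(0.5/0.8) = 0.32 SD
- f = 30%: Φ⁻¹(0.5/0.7) = 0.57 SD

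A 3 SD worsening already almost reaches these caps (0.139 at 10% and 0.316 at 20%).

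**Step 2: against the noise.** The SE of a difference of two medians is √2 × 1.2533 / √26 = 0.348 SD. At f = 20% the cap is 0.32/0.348 = 0.92 SE. Power is about P(Z > 1.96 − 0.92) = 0.15.

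**Step 3: simulated detection, 26 per arm, two-sided permutation test at 0.05.**

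| Share harmed | Median comparison | 75th-percentile comparison |
|---|---|---|
| 10% | about 6-8% | about 11-13% |
| 20% | about 16% | about 39% |
| 30% | about 35% | about 69% |

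With no harm, the median test rejects in about 5% of trials or slightly fewer, so it is correctly sized. Simulating median regression directly gives lower detection (about 2% at 10% harmed and 6-7% at 20%). Those figures are not used: in the hsCRP runs that test rejected in the harmful direction in only 0.7% of null trials, against 2.5% nominal.

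**Step 4: a count above 5 mg/L.** With hsCRP distributions assumed (baseline median 1-3 mg/L, log-SD 0.6-0.9, baseline to week-12 correlation 0.7, a rise of 8 mg/L in harmed women), Fisher's test on new crossings detects about 6-11% at 10% harmed and 19-42% at 20%. If none of 26 women crosses, the upper limit of the exact two-sided 95% interval is 1 − 0.025^(1/26) = 13.2%.

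**The case against.** Several stronger readings are tempting, and the documents do not support them.

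- A reader might infer that a median cannot show harm in a minority at all. It can: it moves, and at 30% harmed it detects the difference in about a third of trials. The accurate statement is very low power, most clearly at 10-20%.
- A reader might infer that the plan set 5 mg/L as a patient-level harm limit and then ignored it. The figure is an assay reference value, printed beside the limit of quantitation. No planned rule was broken. As an endpoint it is also crude: it misses women already above it and rises that stay below it, and it counts 4.9 to 5.1 as harm.
- A reader might take the median as stated for every outcome. For the four markers it is an inference from the PWV and fitness results.
- A reader might treat this as a failed safety objective. Inflammation is a secondary aim, the analysis is described as assessing efficacy, and the conclusion is worded as a suggestion.

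The strongest counter-argument is that the more basic fault lies elsewhere: p > 0.05 with no margin and no interval does not establish absence of worsening at any quantile, and correcting that sentence removes most of the problem. This is right, and the rewording is accordingly the first part of the fix. What remains is that even a well-estimated median would leave the upper tail unexamined. It is also fair that the crossing count is underpowered, so it is kept as description only.

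**Conclusion.** The point holds in limited form. The conclusion on inflammation and oxidative stress goes beyond its support: non-significant comparisons, at the median as far as the text shows, with no interval or margin for any of the four markers. At 26 per arm, a worsening of any size in 20% of exercised women shifts the median by at most 0.32 SD, less than its SE of about 0.35 SD. A non-significant result would be expected in roughly five trials out of six (detection about 16%).

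The caps rest on the normal scale. The detection rates rest also on the 3 SD worsening and on a test without covariates, and the hsCRP crossing rates on assumed distributions. None of this shows that any woman worsened. It shows that the analysis described could not have excluded it.

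**What to change.** 1. Reword the conclusion on the markers to: *no between-group difference in median change was detected; worsening in a minority of women was not excluded.*
2. State the quantile used. For hsCRP, TNF, IL-6 and MPO, report the median difference with its 95% CI and add the 75th-percentile regression with its 95% CI.
3. Run the added analysis in all allocated women with a week-12 value, not only those who met the attendance threshold. Women who stopped attending because they felt worse would otherwise be left out, and BOCF would record them as unchanged.
4. As a descriptive supplement only, report by arm the number moving from ≤5 to >5 mg/L hsCRP, with exact intervals, and label 5 mg/L as the assay's reference limit.

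The cost is a few lines of analysis on data already collected. The 75th-percentile comparison adds little at 10% harmed, and both it and the count will be imprecise at this sample size. The conclusion becomes less favourable.

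### The PWV model leaves out blood pressure, measured with the same device, so baseline pressure can confound the comparison and a pressure change can mask or mimic a stiffness change

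*Combined protocol and SAP*

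**What the plan says.** The primary outcome is arterial stiffness, measured as PWV. Section 5.2 (Primary Outcome Measure) describes the Mobil-O-Graph as a device "whose operation is based on oscillometry recorded by a blood pressure cuff placed on the brachial artery". Under Other Measurements the same device supplies blood pressure: "Blood pressure was measured with Mobil-O-Graph® (IEM GmbH, Stolberg, Germany"). Pressure has no further role in the plan.

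The Statistical Analysis section specifies "quantile regression with baseline values, resting heart rate (bpm) [39], and changes in physical activity", with the terms entered "as potential confounders, after checking baseline group comparisons". The sensitivity analyses are "baseline observation carried forward (BOCF) imputation; per-protocol with minimum attendance of 90%, and complete-case analyses". These deal with missing data and attendance, not with pressure.

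Treatment Allocation and Blinding says that "participants from the city of Granada were included in the exercise group and participants living outside Granada were included in the control group". Matching was attempted on age, BMI and SLEDAI. The Results report no between-group difference in PWV change and conclude that the programme did not worsen arterial stiffness. They contain no blood pressure result.

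**The concern.** PWV reflects the vessel wall and also the pressure distending it when the reading is taken. This is general physiology and not a statement in the documents. Two separate problems follow.

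- **Baseline.** Neither randomization nor direct matching protects against a pressure difference between city residents and those living outside. If baseline pressure predicts later PWV beyond what baseline PWV already captures, the comparison is confounded.
- **Change.** If pressure moves differently in the two groups by week 12, the PWV difference combines a pressure effect with a wall effect. A greater fall with exercise could hide stiffening, and a rise could hide a benefit.

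What is at stake is the wording of the conclusion. A near-zero PWV difference is read as no worsening of stiffness, with no pressure data beside it to support that reading.

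**Working it through.** **The plan's own figures.** Inputs from Sample Size: effect 0.63 m/s, SD 0.75 m/s, power 85%, error 0.05 (taken as two-sided).

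n per group = 2 × (1.960 + 1.036)² × (0.75/0.63)² = 2 × 8.98 × 1.417 = 25.4, rounded up to 26, or 52 in total. This matches the plan, and the present point does not affect it.

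Inputs from Results: difference -0.034 m/s, 95% CI -0.42 to 0.36, p = 0.860. The minus signs are garbled in the text. This reading fits, because the interval's midpoint is -0.03.

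- Half-width = (0.36 + 0.42)/2 = 0.39
- Standard error = 0.39/1.96 = 0.199
- Normal p for 0.034/0.199 = 0.864, close to the stated 0.860

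**Pressure component (assumed inputs).** Let b be the slope of PWV on pressure, and D the difference in pressure change, exercise minus control. The documents give neither. Take b = 0.01 to 0.06 m/s per mmHg and D = 3 to 5 mmHg in either direction.

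Component = b × D, and pressure-free estimate = -0.034 - b × D.

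| b | size of D | component | estimate (shifted CI) if pressure falls more with exercise | estimate (shifted CI) if it rises more |
|---|---|---|---|---|
| 0.01 | 3 | 0.03 | -0.004 (-0.39 to 0.39) | -0.064 (-0.45 to 0.33) |
| 0.01 | 5 | 0.05 | +0.016 (-0.37 to 0.41) | -0.084 (-0.47 to 0.31) |
| 0.03 | 5 | 0.15 | +0.116 (-0.27 to 0.51) | -0.184 (-0.57 to 0.21) |
| 0.06 | 3 | 0.18 | +0.146 (-0.24 to 0.54) | -0.214 (-0.60 to 0.18) |
| 0.06 | 5 | 0.30 | +0.266 (-0.12 to 0.66) | -0.334 (-0.72 to 0.06) |

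The intervals are moved rigidly. They ignore uncertainty in b and D, and simple subtraction is only approximate for a median regression.

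**Thresholds.**

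- The sign changes once a greater fall with exercise exceeds 0.034/b: 3.4 mmHg at b = 0.01 and 0.6 mmHg at b = 0.06.
- For a true effect of -0.63 to appear as -0.034, the component must be 0.63 - 0.034 = 0.596 m/s. That needs 0.596/0.06 = 9.9 mmHg to 0.596/0.01 = 59.6 mmHg, all outside the assumed 3 to 5.
- The shifted lower limit reaches -0.63 at (0.63 - 0.42)/b = 0.21/b: 3.5 mmHg at b = 0.06 and 21 mmHg at b = 0.01. At the steepest slope, therefore, the interval would no longer exclude the design effect, although the estimate stays well short of it.

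**The case against.** The strongest reply is that the primary model is right to leave out week-12 pressure. If exercise changes pressure, and pressure changes PWV, that path is part of the total effect of exercise. This stands: a model with week-12 pressure answers a different question and can only be supportive. The plan does not exclude post-baseline terms on principle, since change in physical activity is one.

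Second, covariates were chosen after comparing the groups at baseline, so pressure may have been examined and found balanced, and matching on age and BMI may have helped indirectly. That is possible, but the documents do not say it, and balance at baseline says nothing about change. Baseline PWV in the model also carries part of any baseline pressure influence. Adjusting for baseline pressure, in turn, does not deal with a pressure change.

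Third, the size is entirely assumed, and even the largest component considered (0.30) is below the half-width (0.39). The upper limit of 0.36 m/s already limits the claim of no worsening, whatever pressure did. This stands too.

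A reader might infer some stronger points that the documents do not support:

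- *The same cuff also recorded resting heart rate.* No device is named for resting heart rate, and the text does not say whether the term is a baseline value or a change.
- *Heart rate was included to correct for conditions during the reading.* It is listed only as a potential confounder, with a citation.
- *Adjusting for pressure would narrow the interval.* The usual least-squares scaling does not carry over to quantile regression. If pressure change differs by group, its correlation with group can offset any gain.

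**Conclusion.** The omission is real and should be corrected. The PWV model, the sensitivity analyses and the matching all leave out pressure, in a non-randomized comparison whose primary outcome depends partly on it. Under the assumed slopes and pressure differences the component is 0.03 to 0.30 m/s, or 5% to 48% of the 0.63 m/s design effect. That is enough to reverse the sign of a -0.034 m/s estimate in most of the range. It is not enough to exceed the interval half-width or to hide the full design effect in the point estimate, and every shifted interval in the table still includes zero.

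It would be tempting to conclude that a pressure fall concealed stiffening, or that a benefit was missed. With no pressure data and no slope, the documents show neither. They show only that the reported PWV result cannot by itself be read as a pressure-independent statement about the vessel wall.

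**What to change.** 1. Add baseline mean or systolic pressure as a covariate in the PWV model. Because results are already known, state that the term was added afterwards.
2. Report the between-group difference in pressure change, with its 95% CI, beside the PWV result. First confirm that week-12 pressure was recorded. The documents give measurement times for physical activity but not for blood pressure, so its availability is inferred from the cuff-based PWV reading.
3. Add one PWV model with baseline and week-12 pressure, labelled supplementary and post hoc.

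The primary model keeps the total effect and sets the primary conclusion. If item 2 or 3 shows a material pressure effect, word the conclusion in terms of PWV and not of pressure-independent stiffness.

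The cost is one paragraph in the analysis plan and a rerun. If the week-12 pressures exist, no new procedure is needed. The downsides are one more covariate in a model planned for about 52 women, and conditioning on a post-treatment value in item 3, which is why that item is supportive only.
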